6.4 Methotrexate (MTX, AMETHOPTERIN) NSC #740 (112004)

6.4.1 Source and Pharmacology:

A folate analogue which inhibits the enzyme dihydrofolate reductase, halting DNA, RNA, and protein synthesis. Initial IV half-life is about 1.2 hours, with a second phase of 10.4 hours. About 50% is bound to protein. Transport into the cell is carrier-mediated. Once in the cell, MTX (Glu)_n are formed, the number of which are related to the cytotoxic effect. Once MTX (Glu)_n are formed, they do not pass back out of the cell unless converted back to MTX. After oral administration, about 60% of a 30 mg/m² dose is rapidly absorbed from the GI tract, with peak blood levels at 1 hour. Above this dose, absorption decreases significantly. Absorption can be very erratic, varying between 23% and 95%. A 20-fold difference between peak levels of drug has been reported (0.1 to 2mM). There is significant enterohepatic circulation of MTX: 9% of MTX is excreted in feces. MTX is excreted unchanged in the urine, except at high doses when it is partially metabolized to hydroxy-MTX and excreted.

6.4.2 Toxicity:

	Common Happens to 21-100 children out of every 100	Occasional Happens to 5-20 children out of every 100	Rare Happens to <5 children out of every 100
Immediate: Within 1-2 days of receiving drug	Nausea, headache	Arachnoiditis: (headache, fever, vomiting, meningismus, nuchal rigidity, and pleocytosis)	Anaphylaxis, vomiting, seizures(L), confusion, back pain, rash, bleeding into subarachnoid or subdural space (risk > with platelet counts < 20,000),

	Common Happens to 21-100 children out of every 100	Occasional Happens to 5-20 children out of every 100	Rare Happens to <5 children out of every 100
Prompt: Within 2-3 weeks, prior to the next course			Myelosuppression, ataxia, somnolence, cranial nerve palsy, subacute myelopathy (paraparesis/paraplegia), speech disorders, pain in the legs, bladder dysfunction
Delayed: Any time later during therapy, excluding the above conditions		Learning disability (L), Cognitive disturbance	Leukoencephalopathy ¹ (L)
Late: Any time after completion of treatment			Progressive CNS deterioration ¹
Unknown Frequency and Timing: Fetal and teratogenic toxicities:			

¹ May be enhanced by HDMTX and/or cranial irradiation. (L)
 Toxicity may also occur later.

6.4.3 Formulation and Stability:

Intact vials may be stored at room temperature (22° -25°C) and are stable for at least 2 years or until date of expiration. IT MTX: Available in various dosages in **preservative-free liquid**, 25 mg/mL in a 2 mL vial, or as a lyophilized powder. Reconstitute the powder with buffered saline solution. The methotrexate solutions may be further diluted with buffered saline or the patient's own CSF. After mixing it should be used within 24 hours, since MTX contains no antibacterial preservative.

6.4.4 Guidelines for Administration:

See Treatment and Dose Modification sections of the protocol.

6.4.5 Supplier:

All forms of methotrexate are commercially available. See package insert for further information.

6.5 Pegaspargase

(Pegaspargase, PEGLA, PEG-L-asparaginase, polyethylene glycol-L-asparaginase, Oncaspar®,) NSC #624239.

6.5.1 Source and Pharmacology:

Pegaspargase is a modified version of the enzyme L-asparaginase. L- asparaginase is modified by covalently conjugating units of monomethoxypolyethylene glycol (PEG), molecular weight of 5000, to the enzyme, forming the active ingredient PEG-L-asparaginase. The L-asparaginase (L-asparagine amidohydrolase, type EC-2, EC 3.5.1.1) used in the manufacture of Pegaspargase is derived from *Escherichia coli* which is purchased in bulk from Merck, Sharp and Dohme. L-asparagine is a nonessential amino acid synthesized by the transamination of L-aspartic acid by a reaction catalyzed by the enzyme L-asparagine synthetase. The ability to synthesize asparagine is notably lacking in malignancies of lymphoid origin. Asparaginase depletes L- asparagine from leukemic cells (especially lymphoblasts) by catalyzing the conversion of L-asparagine to aspartic acid and ammonia. In predominately L- asparaginase naïve adult patients with leukemia and lymphoma, initial plasma levels of L-asparaginase following intravenous administration of pegaspargase were determined. Apparent volume of distribution was equal to estimated plasma volume. L-asparaginase was measurable for at least 15 days following the initial treatment with Pegaspargase. The approximate $t_{1/2}$ in adult patients is 5.73 days. The enzyme could not be detected in the urine. The half-life is independent of the dose administered, disease status, renal or hepatic function, age, or gender. In a study of newly diagnosed pediatric patients with ALL who received either a single intramuscular injection of pegaspargase (2500 IU/m²), *E. coli* L-asparaginase (25000 IU/m²), or *Erwinia* (25000 IU/m²), the plasma half-lives for the three forms of L-asparaginase were: 5.73 ± 3.24 days, 1.24 ± 0.17 days, and 0.65 ± 0.13 days respectively. The plasma half-life of pegaspargase is shortened in patients who are previously hypersensitive to native L-asparaginase as compared to nonhypersensitive patients. L-asparaginase is cleared by the reticuloendothelial system and very little is excreted in the urine or bile. Cerebrospinal fluid levels are < 1% of plasma levels.

6.5.2 Toxicity:

	Common Happens to 21-100 children out of every 100	Occasional Happens to 5-20 children out of every 100	Rare Happens to <5 children out of every 100
Immediate: Within 1-2 days of receiving drug	Allergic reactions (total likelihood of local, and or systemic reaction especially if previous hypersensitivity reaction to native asparaginase), pain at injection site, weakness, fatigue, diarrhea	Allergic reactions (total likelihood of local, and or systemic reaction if no previous hypersensitivity reaction to native asparaginase), rash	Anaphylaxis, hyper/hypotension, tachycardia, periorbital edema, chills, fever, dizziness, dyspnea, bronchospasm, lip edema, arthralgia, myalgia, urticaria, mild nausea/vomiting, abdominal pain, flatulence, somnolence, lethargy, headache, seizures (L), hyperuricemia

	Common Happens to 21-100 children out of every 100	Occasional Happens to 5-20 children out of every 100	Rare Happens to <5 children out of every 100
Prompt: Within 2-3 weeks, prior to the next course	Hyperammonemia (L), coagulation abnormalities with prolonged PTT, PT and bleeding times (secondary to decreased synthesis of fibrinogen, AT-III & other clotting factors) (L)	Hyperglycemia, abnormal liver function tests, pancreatitis (L), increased serum lipase/amylase	Hemorrhage (L), DIC, thrombosis, anorexia, weight loss, CNS ischemic attacks, edema, azotemia and decreased renal function, mild leukopenia, granulocytopenia, thrombocytopenia, pancytopenia, hemolytic anemia, infections (sepsis with/without septic shock, subacute bacterial endocarditis (SBE), URI), CNS changes including irritability, depression, confusion, EEG changes, hallucinations, coma and stupor, paresthesias, hypertriglyceridemia, hyperlipidemia, Parkinson-like syndrome with tremor and increase in muscular tone, hyperbilirubinemia, chest pain
Delayed: Any time later during therapy, excluding the above conditions			Renal failure, urinary frequency, hemorrhagic cystitis, elevated creatinine and BUN, fatty liver deposits, hepatomegaly, liver failure

	Common	Occasional	Rare
	Happens to 21-100 children out of every 100	Happens to 5-20 children out of every 100	Happens to <5 children out of every 100

Unknown Frequency and Timing: Animal reproduction studies have not been conducted with pegaspargase. It is not known whether pegaspargase can cause fetal harm when administered to a pregnant woman or can affect reproduction capacity. However, fetal toxicities and teratogenic effects of asparaginase have been noted in animals. It is unknown whether the drug is excreted in breast milk.

(L) Toxicity may also occur later.

6.5.3 Formulation and Stability

Each milliliter of pegaspargase contains: PEG-L-asparaginase 750 IU ± 20%, monobasic sodium phosphate, USP 1.20 mg ± 5% dibasic sodium phosphate, USP 5.58 mg ± 5%, sodium chloride, USP 8.50 mg ± 5% , Water for Injection, USP qs to 1 mL. The specific activity of pegaspargase is at least 85 IU per milligram protein. Available in 5 mL vials as Sterile Solution for Injection in ready to use single-use vials, preservative free. Keep refrigerated at 2°-8°C (36°- 46°F). Do not use if stored at room temperature for more than 48 hours. **DO NOT FREEZE.** Do not use product if it is known to have been frozen. Freezing destroys activity, which cannot be detected visually.

6.5.4 Guidelines for Administration

For IM administration: the volume at a single injection site should be limited to 2 mL. If the volume to be administered is greater than 2 mL, multiple injection sites should be used. For IV administration: dilute pegaspargase in 100 mL of 0.9% sodium chloride injection (0.9% NaCl) or 5% dextrose injection (D5W) and infuse over 1 to 2 hours through a NS or D5W running infusion line. Pegaspargase admixed in 100 mL of NS or D5W is stable for 48 hours at room temperature. Pegaspargase diluted in 100 mL of 0.9% NaCl is stable for up to 72 hours refrigerated (4°C [39°F]) (refrigerated stability data on file with Sigma-Tau). Avoid excessive agitation. DO NOT SHAKE. Do not use if cloudy or if precipitate is present. Have available during and after the infusion: antihistamine, epinephrine, oxygen, and IV corticosteroids. Observe patient for at least ONE hour after administration for signs of hypersensitivity reactions or per institutional standards.

6.5.5 Supplier:

Commercially available. See package insert for further information.

6.6 ASPARAGINASE Erwinia chrysanthemi (Erwinaze®) or cristantapase (Erwinase®) or Erwinia chrysanthemi (recombinant)-rywn (Rylaze®)

6.6.1 Source and Pharmacology:

L-asparagine is a nonessential amino acid synthesized by the transamination of L-aspartic acid by a reaction catalyzed by the enzyme L-asparagine synthetase. Neoplastic cells associated with acute lymphoblastic leukemia, acute myeloid leukemia and lymphoblastic lymphosarcoma are asparagine-dependent but lack asparagine synthetase activity. The administration of Lasparaginase produces an anti-neoplastic effect by catalyzing asparagine into aspartic acid and ammonia. As a result, these cells lack the ability to produce the asparagine necessary for protein

metabolism and survival. Deamination of glutamine may also play a role in the antineoplastic activity of asparaginase.

Erwinia chrysanthemi [Erwinaze® or Cristantapase (Erwinase®)] is asparaginase derived from cultures of *Erwinia chrysanthemi*. L-asparaginase is a tetrameric enzyme; each of the four identical subunits has a molecular weight of approximately 35 kDa. Asparaginase *Erwinia chrysanthemi* is immunologically distinct from *E. coli* L-asparaginase and may allow continued asparaginase therapy when a hypersensitivity reaction occurs to *Escherichia coli*-derived asparaginase. The package labeling states that there is insufficient information to characterize the incidence of antibodies to asparaginase *Erwinia chrysanthemi*. Several factors are involved in immunogenicity assay results and the assessment of antibodies, including assay methodology, assay sensitivity and specificity, sample handling, timing of sample collection, concomitant medications, and the underlying disease state. The following data have been reported on each of the three preparations of asparaginase:

Clinical Pharmacology of Asparaginase Formulation	Fetal toxicities and teratogenic effects of mitoxantrone have been noted in animals. Toxicities include: low birth weight and prematurity. Mitoxantrone is excreted in human milk and significant concentrations (18 ng/mL) have been reported for 28 days after the last administration.	% Anti-Asparaginase Antibody positive patients
Native Escherichia Coli	26-30 hours	45-75
Pegylated-asparaginase	5.5-7 days	5-18
Erwinia Asparaginase	16 hours (7-13 hrs)	30-50

From: Avramis, V; Panosyan, E; *Pharmacokinetic/Pharmacodynamic Relationships of Asparaginase Formulations: The Past, the Present and Recommendations for the Future. Clin Pharmacokinet* 2005; 44 (4): 367-393.

Effective asparaginase levels have been defined as activity of ≥ 0.1 International Units per mL. Clinical trials with asparaginase *Erwinia chrysanthemi* (Ewinaze) demonstrated that 100% of patients achieved effective asparaginase levels at 48 and 72 hours (n=35 and n=13, respectively) following the third total dose when given on a Monday, Wednesday, Friday schedule. No formal drug interaction studies have been performed with asparaginase *Erwinia chrysanthemi*.

Asparaginase erwinia chrysanthemi (recombinant)-rywn contains an asparagine specific bacterial enzyme (L-asparaginase). L-asparaginase is a tetrameric enzyme that consists of four identical 35 kDa subunits with a combined molecular weight of 140 kDa. The amino acid sequence is identical to native asparaginase *Erwinia chrystanthemi* (also known as crisantapase). The activity of

asparaginase erwinia chrysanthemi (recombinant)-rywn is expressed in units, defined as the amount of enzyme that catalyzes the conversion of 1µmol of L-asparagine per reaction minute, per mg of protein. Asparaginase erwinia chrysanthemi (recombinant)-rywn is produced by fermentation of a genetically engineered *Pseudomonas fluorescens* bacterium containing the DNA which encodes for asparaginase *Erwinia chrysanthemi*.

6.6.2 Toxicity:

	Common Happens to 21-100 children out of every 100	Occasional Happens to 5-20 children out of every 100	Rare Happens to <5 children out of every 100
Immediate: Within 1-2 days of receiving drug		Allergic reactions Anaphylaxis, urticaria	Local injection site reactions, fever
Prompt: Within 2-3 weeks, prior to the next course			Pancreatitis, glucose intolerance, thrombosis, hemorrhage, transient ischemic attack, disseminated intravascular coagulation, hyperbilirubinemia, alanine aminotransferase increased, aspartate aminotransferase increased, hyperglycemia, hyperammonemia, vomiting, nausea, abdominal pain, headache, diarrhea, seizure
Unknown Frequency and Timing: Fetal toxicities and teratogenic effects of L-asparaginase have been noted in animals. It is unknown whether the drug is excreted in breast milk. Adequate, well-controlled studies of asparaginase Erwinia chrysanthemi have NOT been conducted. It is not known whether asparaginase Erwinia chrysanthemi will cause fetal harm or affect the ability to reproduce. It is not known if asparaginase Erwinia chrysanthemi is excreted into breast milk. The use of asparaginase Erwinia chrysanthemi should be avoided in pregnant or lactating patients.			

6.6.3 Formulation and Stability

Asparaginase *Erwinia chrysanthemi* is supplied as a sterile, white lyophilized powder for reconstitution in a clear glass vial with a 3 mL capacity. Each vial contains 10,000 International Units of asparaginase *Erwinia chrysanthemi* and the following inactive ingredients: glucose monohydrate (5.0 mg), sodium chloride (0.5 mg). Store between 2°C and 8°C (36° to 46°F). Store intact vials between 2°C and 8°C (36° - 46°F). Protect from light.

Asparaginase erwinia chrysanthemi (recombinant)-rywn Rylaze®) injection is supplied as a sterile, clear to opalescent, colorless to slightly yellow, preservative-free solution for intramuscular injection.

Each 0.5 mL contains 10 mg asparaginase erwinia chrysanthemi (recombinant)-rywn and the inactive ingredients: polysorbate 80 (0.1 mg), sodium chloride (1.5 mg), sodium phosphate dibasic anhydrous (0.8 mg), sodium phosphate monobasic monohydrate (0.6 mg), and trehalose (32.1 mg). Sodium hydroxide may be added to adjust the pH. The pH is approximately 7.

6.6.4 Guidelines for Administration

Follow manufacturer guidelines for preparation and administration. No more than 2 mL should be given at any one injection site. Doses larger than 2 mL should be divided and given in separate administration sites.

6.6.5 Supplier:

Commercially available. See package insert for further information.

6.7 Mercaptopurine

6.7.1 Source and Pharmacology (MP, purinethol®, 6-mercaptopurine) NSC#000755

Mercaptopurine is an analogue of the purine bases adenine and hypoxanthine. The main intracellular pathway for MP activation is catalyzed by the enzyme hypoxanthine-guanine phosphoribosyl transferase (HGPRT) which catalyzes the conversion of MP to several active nucleotide metabolites including thioinosinic acid, a ribonucleotide which can interfere with various metabolic reactions necessary for nucleic acid (RNA and DNA) biosynthesis. It can also cause pseudofeedback inhibition of the first step in de novo purine biosynthesis or convert to another ribonucleotide which can cause feedback inhibition. Mercaptopurine can be incorporated into DNA in the form of 6-TG nucleotides as well and thus produce toxicity. The absorption of an oral dose of MP is incomplete and variable, with only about 16%-50% of an administered dose reaching the systemic circulation secondary to a first pass metabolism in the liver. Food intake and co-administration with cotrimoxazole (TMP/SMX) significantly reduces absorption of MP. After IV administration, MP has a plasma half-life of 21 minutes in children and 47 minutes in adults. Approximately 19% is bound to protein. Mercaptopurine is well distributed into most body compartments except the CSF. (With high dose IV MP the CSF to plasma ratio is 0.15) MP is metabolized by xanthine oxidase in the liver to 6-Thiouric acid an inactive metabolite. In patients receiving both MP and allopurinol (a xanthine oxidase inhibitor) the dose of MP must be reduced by 50-75%. Since TPMT, 6-thiopurine methyltransferase, is also one of the enzymes involved in the metabolism of MP, those individuals who have an inherited deficiency of the enzyme may be unusually sensitive to the myelosuppressive effects of MP and prone to develop rapid bone marrow suppression following the initiation of treatment. Mercaptopurine is excreted in urine as metabolites and some unchanged drug; about half an oral dose has been recovered in 24 hours. A small proportion is excreted over several weeks.

6.7.2. Toxicology

Incidence	Toxicities
-----------	------------

Common (>20% of patients)	Neutrophil count decreased, white blood cell decreased, anorexia, fatigue
Occasional (4 - 20% of patients)	diarrhea, nausea, vomiting, malaise, oligospermia, infection, fever, platelet count decreased, anemia, mucositis, stomach pain, ulcerative bowel lesion, skin rash, alanine aminotransferase increased, aspartate aminotransferase increased
Rare (≤3% of patients)	Urticaria, skin hyperpigmentation, alopecia, hyperuricemia, hepatic failure, hepatic necrosis, blood bilirubin increased, pulmonary fibrosis, secondary malignant neoplasm, renal toxicity, uricosuria, pancreatitis

Pregnancy Category D

Mercaptopurine can cause fetal harm, including an increased incidence of abortion and stillbirth. Advise women to avoid becoming pregnant while receiving mercaptopurine. Mercaptopurine was embryo-lethal and teratogenic in several animal species (rat, mouse, rabbit, and hamster). It is not known whether mercaptopurine is excreted in human milk; breastfeeding should be avoided.

6.7.3 Formulation and Stability:

Mercaptopurine is available as a 50 mg tablet containing mercaptopurine and the inactive ingredients corn and potato starch, lactose, magnesium stearate, and stearic acid. Store at 15°-25°C (59°-77°F) in a dry place. In the United States, mercaptopurine is also available as an oral suspension in a concentration of 20 mg/mL (2000 mg/100 mL per bottle). The oral suspension is a pink to brown viscous liquid supplied in amber glass multiple-dose bottles with a child resistant closure. It should be stored at 15°-25°C (59°-77°F) in a dry place.

NOTE: the concentration of the commercially available suspension (20 mg/mL) and the compounded suspension (50 mg/mL) are NOT the same; doses should be prescribed in the milligrams required, not mL.

6.7.4 Guidelines for Administration

Guidelines for Administration: See Treatment and Dose Modifications sections of the protocol.

Mercaptopurine should be taken consistently at the same time every day. If allopurinol is also given, the oral dose of mercaptopurine should be reduced by 67-75%. Patients with severe myelosuppression should have their thiopurine S-methyltransferase (TPMT) status and/or their thiopurine metabolite concentrations evaluated, so that the dose of mercaptopurine be reduced in patients with a TPMT defect. Patients with the rare homozygous deficient TPMT phenotype may tolerate only 1/10th to 1/20th the

average mercaptopurine dose. TPMT testing and thiopurine metabolite measurements are commercially available.

6.7.5 Supplier:

Commercially available. See package insert for further information.

Suspension:

For children unable to swallow the tablets whole, a 50 mg/mL oral suspension can be compounded. The suspension is prepared by crushing 50 mercaptopurine 50 mg tablets in a mortar and adding 8.5 mL sterile water for irrigation. The mixture is triturated to form a smooth paste. Next, 16.5 mL simple syrup (pH=7) are added with continuous mixing and finally cherry syrup (pH=7.1) is added to a total volume of 50 mL. The suspension is stable in amber glass bottles at room temperature (19oC -23oC) for up to 5 weeks. The suspension should be shaken well before each use. Procedures for proper handling and disposal of cytotoxic drugs should be used when preparing the suspension. (Aliabadi HM, Romanick M, Desai S et al. Effect of buffer and antioxidant on stability of mercaptopurine suspension. *Am J Health-Syst Pharm.* 65:441-7, 2008).

Supplier: The tablets are commercially available from various manufacturers. In the United States, the commercially available oral suspension is available through AnovoRx Distribution, LLC ([name]). See package insert for further information. **PLEASE NOTE there is a difference in the concentration of the commercially available (20 mg/mL) and extemporaneously compounded (50 mg/mL) oral suspensions.**

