4.0 TREATMENT PROGRAM

The following sections detail the treatment plan for the therapy. Please refer to the Drug Information section for additional administration guidelines. Treatment should begin within three calendar days of enrollment.

There are 3 treatment cohorts on this protocol. Please see protocol sections 2.4.1 and 2.4.2 for review of the experience to date on this protocol.

There will be no inpatient dose escalation or de-escalation.

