Asparaginase Erwinia chrysanthemi (Erwinaze®), crisantapase (Erwinase®) asparaginase Erwinia chrysanthemi (recombinant)-rywn (Rylaze®) may be substituted for allergy to Pegaspargase. See below.

Drug Administration Details:

As per Cohort A, without mitoxantrone

Marqibo®

- Dose Level 1: 1.5 mg/m²/dose (no dose cap) given IV over 60 minutes (±10 minutes) on days 1, 8, 15 and 22.
- Dose Level 2: 2 mg/m²/dose (no dose cap) given IV over 60 minutes (±10 minutes) on days 1, 8, 15 and 22.
- Review list of concomitant medications that are prohibited (CYP3A4 inhibitors) or to be used with caution (Appendix 3). See section 4.5 for drug interactions.
- Dose will be given over 60 minutes ± 10 minutes

Other agents and instructions as detailed above in Cohort A, without mitoxantrone.

Cohort C: Modified Maintenance with Marqibo®

	Day 1	Day 2	Day 3	Day 4	Day 5	Day 8	Daily through day 13	Day 14
Marqibo®	●							Response Evaluator
Dexamathasone	●	●	●	●	●			
Methotrexate (PO)	●					●		
Mercaptopurine (PO)	●	●	●	●	●	●	●	
IT Methotrexate as needed no more than once weekly								

Marqibo®

- Dose Level 1: 1.5 mg/m²/dose (no dose cap) given IV over 60 minutes (±10 minutes) on day 1.
- Dose Level 2: 2 mg/m²/dose (no dose cap) given IV over 60 minutes (±10 minutes) on day 1.
- Review list of concomitant medications that are prohibited (CYP3A4 inhibitors) or to be used with caution (Appendix 3). See section 4.5 for drug interactions.
- Dose will be given over 60 minutes ± 10 minutes

Dexamethasone

- 6 mg/m²/day divided BID given orally on days 1 through 5. The two doses should be separated by at least 8 hours

- Any formulation of dexamethasone is acceptable

Methotrexate

- 20 mg/m²/dose given orally on day 1 and day 8.

Mercaptopurine

- 75 mg/m²/dose/day given orally, daily from days 1-13.

Intrathecal methotrexate

- Given intrathecally as needed, but no more than once weekly. Age-based dosing as below. Alternatively, per standard of care, ARA-C and hydrocortisone may be substituted if methotrexate is contraindicated.
- Timing of IT methotrexate is flexible in regard to timing of Marqibo®. However, these agents should not be given simultaneously in order to reduce the risk of administration route error.

Age (years)	Methotrexate (mg)
1-1.99	8 mg
2-2.99	10 mg
3-8.99	12 mg
≥ 9	15 mg

See appendix 8 for starting dose guidelines.

Dose modifications: (for patients without pre-existing disease related cytopenia)

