4.4 Concurrent Therapy and Drug Interactions

Anti-Cancer Therapy: Concurrent anti-cancer therapy not defined within this protocol, including chemotherapy, radiation therapy, immunotherapy, or biologic therapy may NOT be administered to patients receiving study drug. If these treatments are administered the patient will be removed from protocol therapy.

Investigational Agents: No other investigational agents may be given while the patient is on protocol therapy.

Complementary/Alternative Therapies: Use of complementary/alternative therapies is not specifically prohibited, but is discouraged. All therapies should be reviewed with the study team for the potential of drug interactions with Marqibo® or any of the other chemotherapeutic agents.

Allopurinol: Tumor lysis syndrome prophylaxis should be employed for all patients. Allopurinol should ideally be started at a dose of approximately 100 mg/m²/dose PO TID (maximum dose 600 mg/day/subject) at least 8 hours prior to the first dose of chemotherapy and continue until it is apparent that no tumor lysis has developed after 1 week of treatment. Alternatively, rasburicase may be employed as clinically indicated.

Drug Interactions: No formal drug interaction studies have been conducted with Marqibo®. Marqibo® is expected to interact with drugs known to interact with standard formulation vincristine sulfate. Simultaneous oral or intravenous administration of phenytoin and antineoplastic chemotherapy combinations that included non-liposomal vincristine sulfate have been reported to reduce blood levels of phenytoin and to increase seizure activity. Close monitoring is recommended for subjects taking agents with narrow therapeutic indices and metabolized by the

liver, such as warfarin, phenytoin, quinidine, carbamazepine, phenobarbital, cyclosporine and digoxin.

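### Cohort C: sections 6.7.1 and 6.7.4 give different minimum mercaptopurine reductions with allopurinol (50% and 67%), and the treatment sections state none

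*Combined protocol and SAP*

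**What the plan says.** All references are to the combined protocol and SAP.

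- **Dose.** Section 4.1, Cohort C: "75 mg/m²/dose/day given orally, daily from days 1-13". The dose changes listed there are for low neutrophils or platelets and for liver dysfunction. The section refers to Appendix 8 for starting doses, and Appendix 8 tabulates tablets by body surface area at 75 mg/m².
- **Allopurinol.** Section 4.4: "Tumor lysis syndrome prophylaxis should be employed for all patients". Allopurinol is described first, ideally started at least 8 hours before chemotherapy, to "continue until it is apparent that no tumor lysis has developed after 1 week of treatment". Then: "Alternatively, rasburicase may be employed as clinically indicated".
- **Reduction, pharmacology paragraph.** Section 6.7.1, on patients receiving both drugs: "the dose of MP must be reduced by 50-75" percent.
- **Reduction, administration paragraph.** Section 6.7.4: "If allopurinol is also given, the oral dose of mercaptopurine should be reduced by 67-75" percent. Just above that sentence stands: "Guidelines for Administration: See Treatment and Dose Modifications sections of the protocol".
- **Pointer from the treatment program.** Section 4.0: "Please refer to the Drug Information section for additional administration guidelines".

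**The concern.** Section 6.7.1 explains that xanthine oxidase inactivates mercaptopurine and that allopurinol inhibits this enzyme. The size of the cut is therefore a safety instruction for a myelosuppressive drug; section 6.7.2 lists a decreased neutrophil count among the common toxicities. The protocol sets up the combination itself, because the allopurinol week falls on the first mercaptopurine week.

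There are two difficulties. A site that looks up the rule finds two minimum cuts, and the looser one carries the stronger verb. A prescriber who works only from 4.1, 4.4 and Appendix 8 finds no reduction at all and would prescribe the full 75 mg/m²/day.

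**Working it through.** The plan gives no dose in mg/m² for use with allopurinol, so there is no figure of its own to reproduce. The check is a comparison of texts plus simple arithmetic.

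**Inputs.** Full dose 75 mg/m²/day for 13 days (4.1). Cut of 50-75% (6.7.1) or 67-75% (6.7.4). Allopurinol for about 7 days from the start of treatment (4.4).

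**Step 1. Dose implied by each section.** Dose = 75 × (1 − cut).

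| Cut | Dose, mg/m²/day | Meets 6.7.1 | Within 6.7.4 guideline |
|---|---|---|---|
| 50% | 75 × 0.50 = 37.5 | yes | no |
| 67% | 75 × 0.33 = 24.75 | yes | yes |
| 75% | 75 × 0.25 = 18.75 | yes | yes |

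If 67% is a rounded two-thirds (an assumption), the middle row is 75 / 3 = 25, so about 25 is the sensible reading. The 6.7.4 range lies wholly inside the 6.7.1 range, and 67-75% is the range that satisfies both.

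**Step 2. Size of the mismatch.** 37.5 / 24.75 = 1.52 (1.50 if the divisor is 25). The difference is 37.5 − 24.75 = 12.75 mg/m²/day, and over 7 days 7 × 12.75 = 89.25 mg/m².

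**Step 3. Overlap.** 7 / 13 = 54% of the mercaptopurine days, if allopurinol stops at one week.

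**Step 4. Effect on the course total**, assuming full dose from day 8 and no holds:
- 50% cut: 7 × 37.5 + 6 × 75 = 712.5 mg/m²
- 67% cut: 7 × 24.75 + 6 × 75 = 623.25 mg/m²
- ratio: 712.5 / 623.25 = 1.14

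**Step 5. No reduction applied.** 75 / 24.75 = 3.03, so the full dose is about three times the highest dose within the 6.7.4 guideline on the overlap days.

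**Step 6. Where the rule appears.**

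| Place | Reduction with allopurinol |
|---|---|
| 4.1 Cohort C | none stated |
| 4.3 | none; 4.3.1 to 4.3.5 cover the other drugs and there is no mercaptopurine entry |
| 4.4 | allopurinol prescribed, mercaptopurine not mentioned |
| Appendix 8 | full-dose table only |
| 6.7.1 | 50-75% |
| 6.7.4 | 67-75% |

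**The case against.** The strongest reply is that this is a narrow drafting mismatch with an evident answer. The ranges nest. Section 6.7.4 is the administration paragraph, and 4.0 sends sites to Drug Information for administration guidance, so a careful prescriber reaches 67-75%. The back-reference in 6.7.4 sits next to the rule, so whoever reads one sees the other. Allopurinol is not compulsory, and Cohort C admits patients with disease only at the minimal residual level, so the documents do not show how often it will be used. Complete blood counts are taken twice weekly (7.1), and 4.1 holds mercaptopurine when neutrophils fall below 500/mcL or platelets below 50,000/mcL.

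Much of this stands, and it sets the limits of the point. It does not remove the conflict. Section 6.7.1 says the dose must be cut and gives 50% as the minimum, and no text says which section governs. The hold rule acts only after counts have fallen, and its heading restricts it to patients without pre-existing disease-related cytopenia.

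A reader might infer that a 50% cut breaches a hard ceiling of 24.75 mg/m²/day. The documents do not support that: 6.7.4 says should, and it states no maximum. A reader might also infer that the protocol directs full-dose mercaptopurine with allopurinol. It does not: the treatment sections are silent, and the rule exists where 4.0 points.

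**Conclusion.** The inconsistency is real and should be fixed. Two sections give different minimum cuts for the same drug combination, and the sections a prescriber is most likely to work from give none. On the overlap days the difference is up to 37.5 against about 25 mg/m²/day, or about 1.5-fold. Over the 13-day course it is about 1.14-fold, if full dose resumes on day 8.

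These are ratios of prescribed dose, not estimates of toxicity. They assume allopurinol for 7 days from day 1. They apply only to Cohort C patients who receive it, which could be none to all of the 6 to 12 evaluable patients planned at a dose level.

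Two further inferences are not supported. The documents do not show that a 50% cut is unsafe, nor which range is pharmacologically right; 67-75% is preferred only because it satisfies both sections. Nor do they show an effect on the primary endpoint. Section 9.1.1 counts the share of mercaptopurine doses received, without saying how a reduced dose counts, and none of the figures above bears on that count.

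**What to change.** 1. In 6.7.1, change the range to 67-75%.
2. In 4.1 Cohort C and in the allopurinol paragraph of 4.4, add: *While allopurinol is given, reduce mercaptopurine by 67-75% (see 6.7.4), or use rasburicase instead.*
3. In Appendix 8, note that the table applies only when allopurinol is not given.

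No separate step-up rule is needed. Once allopurinol stops, the 4.1 dose applies, subject to the count and liver rules already in 4.1. Do not write a ceiling of 24.75 mg/m²/day. At a body surface area of 1.00 m², half a 50 mg tablet daily is 25 mg/m²; this is a two-thirds cut, and such a ceiling would exclude it.

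The cost is amendment wording, with no extra patients, procedures or forms. Sites lose the option of a 50-66% cut. Reduced doses may need split tablets or the oral suspension, which 6.7.3 and 6.7.5 already describe.
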